## **9.2. Statistical Analyses**

Demographic and clinical characteristics of the patient population will be summarized using means and standard deviations or medians and interquartile ranges for continuous variables and frequency and percent for categorical variables.

The exercise endurance time (in seconds) will be compared between the two treatments (i.e. Treprostinil and placebo) using an analysis of variance (ANOVA) model for crossover designs. The terms in the model will include sequence, subject within sequence, treatment. Data will be assessed to determine if the normality assumption is plausible. If the normality assumption is not met, transformations will be applied in an attempt to satisfy the assumption (i.e. log, square root, rank). P-values  $<0.05$  will be considered significant.

Secondary outcome variables are continuous and will be analyzed using the ANOVA model for crossover designs as described for the primary outcome variable. For secondary outcome variable in which a baseline measure is taken, the change from baseline value will be used as the outcome variable and will be compared between treatment groups. Normality will be assessed and appropriate transformations used, if needed to satisfy the assumptions of the model. P-values  $<0.05$  will be considered significant.

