### Baseline visit (Visit 1)

- Informed Consent
- Review of Demographics, Medical history, and Medications
- Urine pregnancy testing (for females of childbearing potential)
- Baseline vitals (heart rate, blood pressure, oxygen saturation, height and weight)
- Maximal cardiopulmonary exercise testing/Ramp protocol (including spirometry).
- Venous structure and function testing
- Light meal and rest period.
- Endurance testing at 80% peak exertion to assess baseline measures. (2 hours following maximal exercise testing)
- Adverse event monitoring

Visit 1 is anticipated to take 5-6 hours to complete. At the end of Visit 1, participants will be randomized to one of the two treatment sequences:

1. Treprostinil (Visit 2): placebo (Visit 3) or
2. Placebo (Visit 2): treprostinil (Visit 3).

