## **9. DATA ANALYSIS**

### **9.1. Study Endpoints**

The primary endpoint is exercise endurance time (seconds).

The secondary endpoints are the following:

- Peak VO2
- Ventilator equivalent for CO2 at the lactate threshold
- Oxygen uptake efficiency slope
- Lactate threshold
- Pulmonary blood flow
- Pulse wave velocity
- Augmentation Index
- Shear wave elastography (measure in velocity [m/s]), the mean of 10 measurements will be taken.
- Safety endpoints will include: a drop in systolic systemic blood pressure of greater than 30 mm Hg if SBP >120mm Hg, or a drop in BP to <90 mm Hg if resting BP is less than 120mmHg.

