## **9.3. Sample Size Calculation**

Sample size calculations are based on published literature {Oga et. al. Chest 2003 Jun; 123(6): 1810-6.}. The SD of treatment effect for exercise endurance time is estimated to be 65 second. A sample size of 26 patients is required to have 80% power to detect a change of 37 second using a two-sided test at  $\alpha=0.05$ . This sample size will also provide 80% power to detect an approximate 0.5 m/s change in liver stiffness assuming an SD of 0.75 m/s using the two-sided test at  $\alpha=0.05$ .

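### The crossover ANOVA in Section 9.2 has no period term, so a Visit 2 to Visit 3 effect inflates the error and, if the sequences are unequal, biases the treatment effect

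*Combined protocol and SAP*

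**What the plan says.** Section 9.2 compares endurance time between treprostinil and placebo "using an analysis of variance (ANOVA) model for crossover designs", and the next sentence gives its content: "The terms in the model will include sequence, subject within sequence, treatment". Neither period nor visit appears there or elsewhere in Section 9. Secondary endpoints follow the same route; they "will be analyzed using the ANOVA model for crossover designs as described for the primary outcome variable".

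Under the Visit 1 procedures in Section 6, "At the end of Visit 1, participants will be randomized to one of the two treatment sequences": treprostinil then placebo, or placebo then treprostinil. The treatments are given at Visits 2 and 3, one to two weeks apart. No allocation ratio, blocking or stratification is stated.

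Section 9.3 states: "The SD of treatment effect for exercise endurance time is estimated to be 65 second". It also states: "A sample size of 26 patients is required to have 80% power to detect a change of 37 second using a two-sided test at" the 0.05 level. Section 4.1 plans to enrol exactly 26, so there is no allowance for losses.

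**The concern.** A two-period crossover randomises the order of treatment so that a change over time can be separated from the treatment effect. That separation happens only if period is in the model. The sequence term does not do it: sequence is a between-patient contrast, and the subject terms already absorb it.

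A period effect is plausible here. Endurance time depends on effort and is recorded while the patient is encouraged to keep going. Visits 2 and 3 are each patient's second and third endurance tests. Practice, pacing or confidence could lengthen the later test whatever the treatment.

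Two things are at stake. With equal sequences, the period difference adds to the error variance, so power is lost and intervals are too wide. With unequal sequences, part of the period difference also enters the treatment estimate, with a sign set by which sequence happens to be larger.

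**Working it through.** **Inputs.** From Section 9.3: SD 65 s, effect 37 s, N = 26, two-sided 0.05. From Section 9.2: the model terms. The period effect π (Visit 3 minus Visit 2) and the sequence split are assumptions, because the plan gives neither.

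**Step 1: the plan's own figure.** Read 65 s as the SD of the within-patient treatment difference.
- Normal approximation: ((1.960 + 0.842) × 65/37)² = 24.2, so 25 patients.
- Noncentral t, N = 26, 25 df: standard error 65/√26 = 12.75 s, noncentrality 37/12.75 = 2.90, power 79.7%.

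This agrees with 26 patients and 80% to within rounding. Reading 65 s as the within-patient error SD would need 51 patients, so the first reading is used.

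**Step 2: what the listed model estimates.** Let d be treprostinil minus placebo for one patient, and τ the true effect.
- Treprostinil first (TP): the mean of d is τ − π.
- Placebo first (PT): the mean of d is τ + π.

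The listed model gives the same estimate, t value and df (25) as a one-sample t-test on d; a least-squares fit to simulated data confirmed this. It follows that
- bias = π × (n_PT − n_TP)/N
- effective SD = √(65² + 4π² n_TP n_PT / (N(N − 1)))

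With period in the model, the estimate is the average of the two sequence means of d. Its bias is zero for any split, its standard error is (65/2) × √(1/n_TP + 1/n_PT), and it has 24 df.

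**Step 3: equal sequences, 13/13.** Bias is zero. The effective SD is √(4225 + 1.04π²); for π = 37, √(4225 + 1424) = 75.2 s. Power and type I error without the term are simulated with at least 100,000 runs per setting. Power with the term is from the noncentral t.

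| Assumed π | Effective SD | Power, no period term | Type I error, no period term | Power, period term |
|---|---|---|---|---|
| 0 s | 65.0 s | 79.7% | 5.0% | 79.5% |
| 15 s | 66.8 s | 78% | 4.4% | 79.5% |
| 20 s | 68.1 s | 77% | 4.0% | 79.5% |
| 30 s | 71.8 s | 73% | 3.1% | 79.5% |
| 37 s | 75.2 s | 70% | 2.4% | 79.5% |
| 60 s | 89.3 s | 54% | 0.8% | 79.5% |

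**Step 4: unequal sequences.**
- 14/12: bias is 2/26 = 7.7% of π, which is 2.3 s at π = 30 and 2.8 s at π = 37.
- 16/10: bias is 6/26 = 23% of π, which is 6.9 s at π = 30 and 8.5 s at π = 37. At π = 30, power without the term is about 88% if PT is the larger sequence and about 55% if TP is. Type I error is about 5.7% at π = 30 and 5.7% to 5.9% at π = 37.
- 17/9: bias is 8/26 = 31% of π, which is 11.4 s at π = 37. Type I error is then about 8.6%.

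With the period term, bias is zero and type I error is 5% in each case.

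**Step 5: how likely imbalance is.** If 26 patients were allocated by simple randomisation, the chance of 16/10 or worse is 33%, and of 17/9 or worse 17%. The plan does not say which method is used.

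**The case against.** The strongest case is that the harm is conditional and may be small.

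- **The period effect is unknown.** An effect of 37 s equals the whole target treatment effect, and 60 s is 14% to 25% of a 4 to 7 minute test. At 10 to 15 s the power loss at 13/13 is only 1 to 2 points. This stands; the larger values show sensitivity and are not predictions.
- **The design limits learning.** Each patient does a ramp test and an endurance test at Visit 1, and any adjusted work rate is then kept. This makes a large Visit 2 to Visit 3 effect less likely but does not exclude it.
- **Type I error is not inflated on average.** Averaged over simple randomisation, the listed model holds about 5% and has zero expected bias. This is correct. But the trial yields one split, which will be known, and given that split the estimate is biased unless the sequences are equal. The 8.6% figure needs both a 17/9 split and a 37 s effect; with blocking and few losses neither bias nor inflation would be material.
- **The term is not free.** With no period effect, power with it is 77% at 16/10 and 75% at 17/9, against 80% without. Averaged over simple randomisation it is 78% against 80%, and the two models break even near a 15 s period effect. This stands.
- **The wording may not be exhaustive.** A model described as a crossover ANOVA may have been meant to include period. The sentence nevertheless lists the terms, and an analyst following it would leave period out. Adding it after the data are seen would be an unplanned change to the primary analysis.

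Section 2.3 calls the study a pilot, but Section 9.3 powers a formal test at 80% with no reserve.

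**Conclusion.** The concern holds. As written, the primary analysis and every secondary analysis are paired t-tests that make no adjustment for period. The algebra does not depend on any assumed value; the size of the harm does.

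Near balance, the cost is lost power and wide intervals: 1 to 2 points of power for a period effect up to 15 s, about 7 points at 30 s and 10 points at 37 s. Bias becomes material only when a clear imbalance meets a sizeable period effect; at 16/10 and 30 s it is 6.9 s, or 19% of the 37 s target. These figures assume normal differences with SD 65 s and no carryover.

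**What to change.** In Section 9.2, list the model terms as sequence, subject within sequence, period (Visit 2 or Visit 3) and treatment, and state that this applies to the primary and all secondary endpoints. Make the change before unblinding.

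It also helps to state 1:1 blocked allocation to the two sequences, if that is what was used. Blocking keeps the loss from the extra term small, but it does not replace the term, because balance removes the bias and not the inflated error.

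The cost is one error df (25 to 24). With no period effect, power goes from 79.7% to 79.5% at 13/13 and to 77% at 16/10. The noncentral t sample size is 27 with either df, so the term does not change the number of patients needed. Study conduct and data collection are unaffected.

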## 2.3. Rationale for the Study

In this pilot study we propose to explore the effects of a locally delivered inhaled pulmonary vasodilator (inhaled treprostinil) on exercise performance, pulmonary blood flow, venous pressure response and vascular function in stable Fontan patients. We will also assess the effects of resting and acute rises in exercise induced systemic venous pressure on liver stiffness and will also assess whether treprostinil will attenuate the acute stiffness increase that we expect to see.

Specifically we will target the following endpoints in order to achieve these objects: exercise endurance (primary endpoint), and secondary endpoints including: systemic venous pressure, liver stiffness, peak VO2, VE/VC02 slope, Anaerobic threshold, Oxygen uptake efficiency slope, anaerobic threshold, Qp (pulmonary blood flow), augmentation

index, pulse wave velocity, flow mediated dilatation and laser flow Doppler %flow increase. We plan to use a prospective, randomized, double-blinded, placebo-controlled, crossover design.

The rationale for selecting these primary and secondary endpoints and trial design, is to identify potential predictors of responders to inhalation delivered pulmonary vasodilator therapies. Baseline hemodynamic and exercise characteristics may permit identification of factors associated with positive response in the primary outcome measure.

The Principal Investigator, at his previous institution, developed a novel, simple and safe non-invasive screening tool for estimating pulmonary arterial responses to exercise by measuring peripheral venous pressures in the upper limb. In the absence of pathway obstruction, venous pressures accurately reflect central pulmonary arterial pressures in Fontan patients. This system will be used to assess hemodynamic responses to pulmonary vasodilator therapy and will better classify which subset of patients has a more vigorous response.

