#### Secondary Research Hypotheses:

- Inhaled treprostinil will increase peak VO2 relative to placebo
- Inhaled treprostinil will decrease ventilatory equivalent for CO2 at the lactate threshold (VE/VCO2 at LT) and at peak exercise relative to placebo.
- Inhaled treprostinil will result in a higher estimated lactate anaerobic threshold relative to placebo
- Inhaled treprostinil will result in a superior oxygen uptake efficiency slope
- Inhaled treprostinil will result in an increase in pulmonary blood flow. We hypothesize that this effect will be more pronounced in patients noted to have a

more elevated rate of rise in systemic venous pressures with exercise at baseline relative to placebo

- Inhaled treprostinil will improve exercise related changes in rate of rise of systemic venous pressures
- Inhaled treprostinil will result in improved vascular function tests, specifically pulse wave velocity, and brachial flow mediated dilatation.
- Higher resting venous pressures will be associated with a greater degree of liver stiffness, and greater rises in venous pressures will induce proportional rises in liver stiffness
- Inhaled treprostinil will attenuate the degree of exercise induced acute liver stiffness

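### Section 9.2 calls every secondary outcome significant at an unadjusted P<0.05, with no hierarchy and no exploratory label, although section 2.3 describes an exploratory pilot

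*Combined protocol and SAP*

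**What the plan says.** Section 9.1 names one primary endpoint: "The primary endpoint is exercise endurance time (seconds". Under "The secondary endpoints are the following" it then lists eight efficacy measures and one safety item. The eight are peak VO2, ventilatory equivalent for CO2 at the lactate threshold, oxygen uptake efficiency slope, lactate threshold, pulmonary blood flow, pulse wave velocity, augmentation index and liver shear wave speed.

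Section 9.2 treats them as it treats the primary: "Secondary outcome variables are continuous and will be analyzed using the ANOVA model for crossover designs as described for the primary outcome variable". The paragraph on the primary and the paragraph on the secondaries both carry the rule "P-values $<0.05$ will be considered significant". No section gives a testing order, an adjustment, a condition on the primary result, or a plan to report confidence intervals.

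Section 2.3 sets a different tone: "In this pilot study we propose to explore the effects". Its own endpoint list, which begins "exercise endurance (primary endpoint), and secondary endpoints including: systemic venous pressure, liver stiffness", is longer than the list in section 9.1. It adds venous pressure, flow mediated dilatation and laser Doppler flow.

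**The concern.** Section 9.2 is a decision rule, not just missing detail: it says which secondary results will be called significant. Two other places suggest that the secondaries are meant as formal tests. The Secondary Research Hypotheses in section 3 are directional, for example "Inhaled treprostinil will increase peak VO 2 relative to placebo". Section 9.3 also gives liver stiffness, a secondary endpoint, its own power statement with a two-sided test at 0.05.

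With eight or more such tests and no rule linking them, the chance that at least one crosses 0.05 when the drug does nothing is well above 5%. A reader of the trial report would have no basis in the plan for treating such a result as provisional. What is at stake is how far any secondary finding can be believed, for instance on liver stiffness or peak VO2.

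**Working it through.** **Inputs**
- Level per test: 0.05 (section 9.2). Section 9.3 is two-sided; section 9.2 does not say, so two-sided is carried over.
- Patients: 26, each receiving both treatments (sections 4.1 and 9.3).
- Number of secondary tests, k: 8 from section 9.1, and 11 distinct endpoints from section 2.3, where anaerobic threshold appears twice. Each endpoint counts as one test.
- Correlation between outcomes, rho: not in the documents. Assumption: one common value, varied from 0 to 0.9.

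**The plan's own figure.** Section 9.3 claims "80% power to detect a change of 37 second using a two-sided test at $\alpha=0.05" with 26 patients and an SD of 65 s. Reading 65 s as the SD of within-patient differences, the noncentrality is (37/65) × √26 = 2.90. Power is 79.7% on 25 degrees of freedom, or 79.5% on 24. The stated 80% is reproduced. The full 0.05 is spent on one primary test, so the number of secondaries does not alter its error rate.

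**Independent outcomes, no drug effect.**
- Any significant secondary, either direction: 1 − 0.95^k. For k = 8 this is 33.7%; for k = 11 it is 43.1%.
- Any significant secondary in the favourable direction: only one tail of each two-sided test counts, so 1 − 0.975^k. For k = 8 this is 18.3%; for k = 11 it is 24.3%.

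**Correlated outcomes.** For each setting, 40,000 null trials were simulated, each with 26 within-patient differences on k equally correlated outcomes. Each outcome was tested by a paired t-test on 25 degrees of freedom and oriented so that benefit is positive. The row for rho = 0 uses the formulas above; simulation agrees with them to within about 0.2 percentage points.

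| rho | k = 8, either direction | k = 8, favourable | k = 11, either direction | k = 11, favourable |
|---|---|---|---|---|
| 0 | 33.7% | 18.3% | 43.1% | 24.3% |
| 0.3 | 29.8% | 15.2% | 38.2% | 19.3% |
| 0.5 | 25.1% | 12.7% | 30.6% | 15.2% |
| 0.7 | 19.5% | 9.8% | 22.8% | 11.2% |
| 0.9 | 12.1% | 6.0% | 13.4% | 6.6% |

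**Scale.** One two-sided test at 0.05 has a 2.5% chance of a false favourable result. For rho from 0.7 to 0, the eight endpoints raise this by a factor of 9.8/2.5 = 3.9 to 18.3/2.5 = 7.3. For comparison, a Bonferroni or Holm rule over the eight would start at 0.05/8 = 0.00625. The chance of any false significant secondary would then be 1 − (1 − 0.00625)^8 = 4.9% under independence.

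**The case against.** **Pilot framing.** The strongest defence is that this is a 26-patient pilot with one primary endpoint, and unadjusted secondary P-values in such a study are commonly read as nominal. That supports a light remedy and argues against imposing an adjustment. It does not remove the problem, because section 9.2 does not carry the framing of section 2.3 into how secondary P-values are read, and section 9.3 attaches a formal test to one of them.

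**Correlation.** Several outcomes come from exercise testing of the same patients, so independence is unlikely and the upper ends of the ranges are probably too high. This stands, and is why ranges are given. At a correlation of 0.9 the either-direction figure for eight endpoints is 12.1%.

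**Repeated measurements.** Flow is measured at rest and at peak exercise, and stiffness and pulse wave velocity before and after exercise, which could suggest more tests than counted here. Section 9.2 analyses change from baseline where a baseline exists, which may merge some of these pairs, although it does not define the baseline. The count was therefore not raised.

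**Two stronger readings.** A reader might take 20-40% as the chance of a false secondary benefit. The documents do not support that: such figures count apparent harm as well as benefit. In the favourable direction the eight endpoints of section 9.1 stay below 20% even if independent, and the eleven of section 2.3 reach at most 24.3%. A reader might also infer that a failed primary could be replaced by whichever secondary succeeds. Nothing in the documents permits this; they fix one primary endpoint and size the trial on it.

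**Conclusion.** The point holds for the secondary outcomes only. With no drug effect, the plan as written has about a 20-34% chance of declaring at least one of the eight endpoints in section 9.1 significant in either direction, and about a 10-18% chance of one in the favourable direction. For the eleven in section 2.3 the figures are about 23-43% and 11-24%.

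These figures rest on two-sided tests, one test per endpoint, and an assumed common correlation of 0.7 down to 0. Higher correlation would lower them. Given the single primary and the pilot setting, this is a change that should be made because it is cheap and alters what the trial can claim. It is not a flaw in the primary analysis.

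**What to change.** In section 9.2, replace the second occurrence of "P-values $<0.05$ will be considered significant", in the paragraph on secondary outcomes, with: *Secondary outcomes are exploratory; they will be reported as treatment differences with 95% confidence intervals, and any P-values are nominal and not adjusted for multiplicity.* The rule for the primary stays as it is.

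This costs one sentence and changes no sample size, visit or procedure. The downside is that secondary results, including liver stiffness, can no longer be called significant on an unadjusted P-value. The change does not lower the percentages above; it stops a nominal crossing of 0.05 from being declared a finding.

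If the sponsor wants a formal secondary claim, it should name that endpoint in section 9.1 and test it only after a significant primary result. This is a trade-off for the sponsor, since the claim is then lost whenever the primary fails. Venous pressure would first have to be added to section 9.1, which does not list it now.

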## **9.3. Sample Size Calculation**

Sample size calculations are based on published literature {Oga et. al. Chest 2003 Jun; 123(6): 1810-6.}. The SD of treatment effect for exercise endurance time is estimated to be 65 second. A sample size of 26 patients is required to have 80% power to detect a change of 37 second using a two-sided test at  $\alpha=0.05$ . This sample size will also provide 80% power to detect an approximate 0.5 m/s change in liver stiffness assuming an SD of 0.75 m/s using the two-sided test at  $\alpha=0.05$ .

# **10. RISKS AND BENEFITS**

## **10.1. Potential Benefits**

There is potential for direct benefit for participating in this study. If a participant demonstrates hemodynamic improvement (i.e. lower systemic venous pressures, or greater pulmonary blood flow) from drug therapy, their cardiologists would be notified at the end of the study to discuss longer term pulmonary vasodilator therapy. For participants with unexpected high baseline systemic venous pressures, the clinical implications will be assessed and discussed with the patient and their cardiologist as to whether this needs further diagnostic exploration. In addition, the information learned from this research study may benefit Fontan patients in the future.

